### Dose-Response Analysis

To demonstrate the dose-response relationship between CCX140-B treatment (including placebo) and the primary endpoint, a Multiple Comparison Procedure – Modelling (MCP-MOD) approach (Bretz et al., 2005) will be carried out. This analysis allows for uncertainty in the dose-response relationship through inclusion of contrasts from multiple pre-specified candidate models to assess dose-response. If a dose-response relationship exists, then the primary efficacy endpoint will be estimated in each of the treatment groups using the selected dose-response models. Four candidate models will be considered for the primary analysis. The models include a linear model, a logistic model, a quadratic model and an Emax model. Within each model, dose-response will be tested using dose levels of 0 (placebo), 1 (CCX140-B 5mg), 2 (CCX140-B 10mg) and 3 (CCX140-B 15mg).

The MCP-Mod procedure requires pre-specified parameter estimates for the candidate models based on available information in order to derive optimum contrast coefficients for testing the null hypothesis that a dose-response does not exist in any of the candidate models. The procedure will be carried out by the R package MCPMod (Bornkamp et al., 2017).

Point estimates and the corresponding 90% CIs from the selected dose-response models will be displayed.

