The changes in RBC parameter findings are likely translatable to humans, but are monitorable, reversible, and there was an acceptable safety margin across all species (see below). To ensure early detection of **changes in RBC parameters** in the Phase 2 clinical trial, blood samples will be drawn at baseline, at 6 hours following administration of the first dose, at Study Days 8, 15 and 29, then at every 4 week intervals throughout the treatment and follow up period for assessment of complete blood count, reticulocyte count and bilirubin.

Neuropathy findings in dogs are likely species-specific with a higher safety margin than **the changes in RBC parameters**, however reversibility was incomplete and the mechanism is unknown. Subjects in the Phase 2 study will be monitored for adverse events related to the nervous system, and will be **examined for vibration-sense deficits and** evaluated for early symptoms using a questionnaire validated for early detection of peripheral neuropathy in studies of patients with HIV infection.

The NOAEL in the 26-week rat studies of 15 mg/kg/day (based on reversible **changes in RBC parameters**) was associated with systemic AUC₀₋₂₄ total plasma exposures to CCX140 of 464.6 and 493.7 $\mu\text{g}\cdot\text{hr}/\text{mL}$, for males and females, respectively. Thus, for dose escalation in human subjects, exposures to CCX140 should not exceed total plasma AUC₀₋₂₄ exposures of 465 $\mu\text{g}\cdot\text{hr}/\text{mL}$, or total C_{max} concentrations of 32 $\mu\text{g}/\text{mL}$.

Results from all the safety and toxicology studies support repeated dosing of CCX140-B to humans up to predicted exposure parity with the 26-week rat NOAEL levels. The NOAEL in the 26-week rat study was associated with systemic exposure to CCX140 which was approximately 3- to 4-fold the predicted human exposure with a 15 mg twice daily (b.i.d.) dose of CCX140-B.

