6.4. Rationale for Dose Selection

The three active treatment doses proposed for the study are 5 mg administered daily, 10 mg administered twice daily, and 15 mg administered twice daily.

Five (5) mg daily is selected as the lowest dose that was tested and found to be both safe and to be associated with a clinically-meaningful therapeutic effect in subjects with diabetic nephropathy (DN) in Study CL005_140. A total of 332 subjects were enrolled in a randomized, double-blind, placebo-controlled clinical trial to evaluate the efficacy, safety and tolerability of 5 mg CCX140-B 5 and 10 mg CCX140-B compared to placebo, when administered for up to 52 weeks in subjects with DN. The Phase 2 trial met its primary endpoint by demonstrating that treatment with 5 mg of CCX140-B given orally once daily added to a standard of care (SOC) regimen of RAAS blockade treatment resulted in a statistically significant ($p=0.01$) improvement in UPCR, beyond that achieved with SOC alone. The maximum treatment effect (24% reduction) was reached at 12 weeks, and sustained reduction in albuminuria relative to placebo was observed over the full year (UACR at each one of the ten time points over the 52-week treatment period in the subjects who received 5 mg CCX140-B continuously for 52 weeks, were below

those of the SOC alone group). Both active treatment regimens were well-tolerated; no dose-related safety signals were reported.

Ten (10) mg twice daily is selected as an intermediate dose for exploration of dose response and to guard against losing the efficacious dose if 15 mg twice daily is associated with unexpected or intolerable toxicity. Using the rat as the more sensitive species based on exposure, the NOAEL in the 26-week rat study was 15 mg/kg/day. The NOAEL in the 13-week and 26-week rat studies were associated with systemic exposures to CCX140 which were about 9-10 times higher than the human exposure associated with a daily 10 mg dose, and about 4-5 fold a 10 mg BID dose.

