Fifteen (15) mg twice daily is selected as the highest dose for this protocol, which is projected to provide exposure at both peak and trough that is within the safety margins established in the toxicology program, and that is projected to maintain a high level of target engagement, as summarized below and detailed in the Investigator's Brochure. The projected clinical exposure with 15 mg twice daily dosing is 3-fold below the NOAEL exposure established in the most sensitive species tested in the nonclinical toxicity studies (rat 26-week, PO, QD). In humans, CCX140-B has been administered and was well tolerated at 15 mg administered once daily for up to 10 days in healthy volunteers, and at 10 mg administered once daily for up to 52 weeks in subjects with DN. Administration of 15 mg twice daily in humans without proteinuria is projected to achieve a peak concentration of ~6500 ng/mL (~13 μ M) and a trough concentration of ~5500 ng/mL (~11 μ M) at steady state. Total exposure with 15 mg twice daily is projected to be ~2-fold higher than that achieved with 15 mg daily administration in healthy volunteers and 3.07-fold higher than that observed with 10 mg daily exposure in subjects with DN. Trough exposure with 15 mg twice daily is projected to be 2.4-fold higher than trough exposure achieved in DN.

Rationale for selection of 15 mg twice daily is to ensure adequate exposure margin to address:

1. Loss of albumin-bound drug through proteinuria; a post-hoc analysis PK in subjects of trial #CL005_140 who entered in study with albuminuria >1 gram indicated exposure was approximately 30% below the mean for the treatment group as a whole
2. Increased binding competition from endogenous ligand; MCP-1 is reported to be increased in serum and urine in subjects with FSGS

Rationale for administration of the highest dose as a divided dose (15 mg twice daily), as opposed to a single dose (30 mg once daily) include:

1. Ease of administration (3 tablets twice daily vs 6 tablets once daily)
2. 15 mg administered as a single daily dose has previously been tested and tolerated in healthy volunteers, while 30 mg has not been previously dosed
3. 15 mg twice daily will result in a lower C_{max} than 30 mg once daily, mitigating the potential for C_{max} -driven safety concerns

To ensure early detection of dose-related safety signals, the proposed protocol will incorporate:

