## 2.2 Study Design

### 2.2.1 Overview

This study will evaluate the efficacy, safety, tolerability, and pharmacokinetics of up to 12 weeks of treatment with each of three dose regimens of CCX140-B or placebo, when used in combination with stable standard of care therapy in subjects with FSGS with significant proteinuria, assessed as UPCR > 1g/g at Screening.

The target is to enroll 40 adult male or female subjects in this randomized, double-blind, placebo-controlled, Phase 2 study. Subjects will be randomized 1:1:1:1 to one of four treatment groups:

- Group A: Placebo (N=10)
- Group B: CCX140-B 5 mg once daily (N=10)
- Group C: CCX140-B 10 mg twice daily (N=10)
- Group D: CCX140-B 15 mg twice daily (N=10)

[figure not shown]
Subjects will be screened within a period not to exceed 28 days prior to Study Day 1 (the first day of dosing). All subjects will take blinded study medication in the morning and evening, with or without food, for 84 consecutive days. Following the 84-day blinded dosing period, all subjects will take open label CCX140-B for an additional 84 days at the highest dose under evaluation, currently planned to be 15 mg twice daily.

During the treatment period, eligible subjects will visit the study center on Study Days 1, 8, 15, 29 (Week 4), and Weeks 8, 12 (primary endpoint), 13, 16, 20, and 24 for study procedures including interval history, physical examination and vital signs, ECG, study questionnaires, and collection of blood and urine. Subjects will discontinue study drug as of Study Day 169 (Week 24) and will return for a follow up visit on Week 28. When feasible, upon discontinuation of treatment for any reason a sample of whole blood should be collected for assessment of elimination 2, 7 and 14 days after the final dose of CCX140-B (or placebo).

A study schema is depicted in Figure 1. All study procedures are presented in Table 1.

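### The MCP-Mod dose axis in SAP 3.4.1 (0, 1, 2, 3) follows mg per intake and ignores dosing frequency; the regimens are 0, 5, 20 and 30 mg/day, and nothing justifies the equal spacing (minor)

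*SAP*

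**What the plan says.** SAP 3.4.1 (Dose-Response Analysis) adds an MCP-Mod analysis of the primary endpoint with linear, logistic, quadratic and Emax candidates. It fixes the axis: "dose-response will be tested using dose levels of 0 (placebo), 1 (CCX140-B 5mg), 2 (CCX140-B 10mg) and 3 (CCX140-B 15mg". The labels carry no dosing frequency. The models are then used for estimation: "If a dose-response relationship exists, then the primary efficacy endpoint will be estimated in each of the treatment groups using the selected dose-response models", with point estimates and 90% CIs displayed.

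SAP 2.2.1 defines the regimens: "Group B: CCX140-B 5 mg once daily (N=10" and "Group C: CCX140-B 10 mg twice daily (N=10", with the top arm at 15 mg twice daily. Protocol 4.1 (Table 1) and SAP 2.2.2 agree. SAP 6 records only that MCP-Mod was added at the sponsor's request. No section gives a reason for equally spaced dose levels.

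**The concern.** All four candidate models are parametric in dose, so the numbers chosen for the axis enter the fitted curve. The codes space the arms 1:1:1, whereas the daily doses space them 5, 15 and 10 mg apart, or 1:3:2. Slope or ED50 parameters cannot absorb this, because one set is not a linear rescaling of the other. Elsewhere the SAP does separate the once-daily arm from the twice-daily arms: in the trough sampling windows (3.5.1) and in the choice between AUC0-12 and AUC0-24 (3.5.3).

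At stake are the model-based arm estimates and intervals in a study titled dose-ranging, mainly for the 5 mg once-daily arm, which is the only arm whose relative position changes.

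**Working it through.** **Inputs.** Codes from SAP 3.4.1. Regimens from SAP 2.2.1. SD 0.70 for log UPCR change, 10 per arm and a treatment/placebo ratio of 0.5 from SAP 2.2.4 and Protocol 9.4. Two-sided alpha 0.10 from SAP 3.1.5.

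**The plan's own figure.** The documents give no number for MCP-Mod. The stated precision reproduces with 0.70 as the within-arm SD: t(0.95, 18 df) × 0.70 × √(2/10) = 0.543, and 0.5 × exp(±0.543) = (0.29, 0.86).

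**The axis.**

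| Arm | mg per intake / 5 | mg/day | Position on codes | Position by mg/day |
|---|---|---|---|---|
| Placebo | 0 | 0 | 0 | 0 |
| 5 mg once daily | 1 | 5 | 1/3 | 1/6 |
| 10 mg twice daily | 2 | 20 | 2/3 | 2/3 |
| 15 mg twice daily | 3 | 30 | 1 | 1 |

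**Exposure in the protocol.** Protocol 6.4 puts the rat NOAEL exposure at "about 9-10 times higher than the human exposure associated with a daily 10 mg dose, and about 4-5 fold a 10 mg BID dose". Twice-daily 10 mg therefore gives 10/5 = 2.0 to 9/4 = 2.25 times the exposure of once-daily 10 mg; mg per intake would give 1. Total exposure at 15 mg twice daily is projected to be "3.07-fold higher than that observed with 10 mg daily exposure in subjects with DN"; the daily-dose ratio is 3.0 and the per-intake ratio 1.5. Protocol 2.4 is consistent, with the NOAEL exposure at "approximately 3- to 4-fold the predicted human exposure with a 15 mg twice daily (b.i.d.) dose of CCX140-B": 10/4 = 2.5 to 9/3 = 3.0 times 10 mg daily. For trough, "Trough exposure with 15 mg twice daily is projected to be 2.4-fold higher than trough exposure achieved in DN"; the comparison dose is not named and is read here as 10 mg daily. If 5 mg daily gives half the exposure of 10 mg daily (assumption), 5 mg once daily sits at 0.5/3.07 = 0.16 of the top arm by total exposure and 0.5/2.4 = 0.21 by trough. Neither is near 0.33.

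**Illustration: response linear in mg/day, ratio 0.5 at 30 mg/day.**

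- True log means: ln(0.5) × (0, 5, 20, 30)/30 = 0, −0.116, −0.462, −0.693. The true reduction at 5 mg once daily is 1 − exp(−0.116) = 10.9%.
- Least-squares line on the codes: slope −1.213/5 = −0.2426, mean −0.318. Fitted placebo is +0.046 and fitted 5 mg once daily is −0.196.
- Arm estimate: 1 − exp(−0.196) = 17.8% against 10.9%, an error of 0.081 log units. SE = 0.70 × √(1/40 + 0.25/50) = 0.121. The nominal 90% CI covers the arm mean in about 83% of trials.
- Relative to fitted placebo: 1 − exp(−0.2426) = 21.5% against 10.9%. SE = 0.70/√50 = 0.099. The expected 90% CI for the ratio is 0.664 to 0.927, with about 65% coverage.
- The same model on mg/day recovers the means exactly, and both coverages are 90%.
- Other arms relative to placebo move little: ratios 0.616 against 0.630 and 0.483 against 0.500.

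**Trend test, same truth.** The two linear contrasts correlate 0.984. Power is 77.6% on codes and 78.7% on mg/day (36 df, one-sided 5%). Type I error is unaffected, because a flat response is flat on any axis.

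**Saturating shapes.** Four models were fitted to 40,000 simulated trials per truth and the lowest AIC chosen. AIC and the ED50 bound (1.5 times the top dose) are assumptions, since the SAP states neither. RMSE of the 5 mg once-daily arm mean, in log units (raw arm SE 0.70/√10 = 0.221):

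| Truth on mg/day | Codes | mg/day |
|---|---|---|
| Linear | 0.172 | 0.162 |
| Emax, ED50 20 | 0.172 | 0.174 |
| Emax, ED50 10 | 0.172 | 0.182 |
| Emax, ED50 5.8 | 0.178 | 0.193 |
| Emax, ED50 5 | 0.179 | 0.195 |

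**The case against.** The strongest reply is that no harm to estimation has been shown. Only the linear truth favours mg/day in the table above, by 0.010 log units. Protocol 2.4.1 hints at saturation in diabetic nephropathy. Overall placebo-corrected UACR reductions were 1 − 0.82/0.98 = 16.3% at 5 mg and 1 − 0.89/0.98 = 9.2% at 10 mg. In the high-albuminuria subset the log effects were ln(1.45/0.77) = 0.63 and ln(1.45/0.61) = 0.87, a ratio of 1.37 where linearity would give 2. If a linear model is fitted when the truth is Emax with ED50 10 mg/day, the 90% CI for the 5 mg once-daily arm covers 89.5% on codes and 82.7% on mg/day. This stands. A reader might infer that daily dose would give more accurate estimates, and the documents do not support that. They do not support the codes either: in those cases a misplaced axis partly offsets a wrong or unstable model choice. When the Emax model matches the truth, mg/day recovers the arm means exactly and the codes do not.

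A reader might also take 21.5% against 10.9% as the error in the displayed estimate. It is not. SAP 3.4.1 displays arm estimates, for which the figure is 17.8%; 21.5% is relative to fitted placebo and adds the misfit at placebo.

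The reach is narrow. MCP-Mod is an added analysis in an exploratory study. The MMRM treats treatment as a class factor, so axis-free arm comparisons are reported anyway. No ED50 or target dose is a listed output. SAP 3.5.3 plans a separate exposure-response report.

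Reading the codes as ordinal labels does not help, since these models have no ordinal form. SAP 7 refers to separate programming specifications, which may hold model settings, but SAP 3.4.1 itself fixes the axis.

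**Conclusion.** The point holds as a minor one. The axis reflects mg per intake, departs from both daily dose and the protocol's exposure figures, and is not justified anywhere. The model-based arm estimates and 90% CIs depend on it.

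The 17.8% against 10.9% result rests on an assumed response linear in mg/day, a 50% reduction at 30 mg/day, SD 0.70, 10 per arm and a selected linear model. The documents give no dose-response shape in FSGS, so the size and direction of the error in the actual trial are unknown.

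A reader might go further and infer that the dose-response test or the primary comparisons are invalid. They are not: the trend test keeps its type I error and changes by about one power point, and the MMRM does not use the axis. What is gained by changing it is a correct, stated scale.

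**What to change.** Before unblinding, replace the dose levels in SAP 3.4.1 with total daily dose: 0, 5, 20 and 30 mg/day. Alternatively, state and justify an exposure-based axis, for example Day 15 total exposure or trough. Derive the candidate-model parameter guesses and optimal contrasts on the chosen scale, and state the model selection criterion.

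The cost is about one sentence in the SAP and a changed dose vector in the R call, with no new data. It alters the analysis scale only, not any dose given.

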9.4. Sample Size Justification

Assuming the standard deviation (SD) for the change from baseline in the logarithmic transformation of UPCR is 0.70, with 10 subjects per treatment group, the 90% confidence interval (CI) for the between group difference in the log scale will have a $\frac{1}{2}$ width of 0.543. In other words, if the ratio of the treatment over placebo is 0.5 (50% reduction from placebo) in UPCR, the 90% CI will be (0.29, 0.86) (i.e., 14% to 71% reduction).

Assuming SD =8.5 for change from baseline in eGFR, with 10 subjects per group, the 90% CI for the between group difference will have a $\frac{1}{2}$ width of 6.6. If the difference between treatment and placebo is observed to be 10 mL/min/1.73m², the 90% CI will be (3.4, 16.6).

Note the above calculation is based on the SD estimated from Study CL005_140 and an unadjusted 2-sided alpha of 10%.

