### 3.1.5 *Hypothesis Testing*

As this is an exploratory study in a rare disease, unless specified otherwise, all statistical tests and confidence intervals will be based on a 2-sided alpha of 0.10. No multiplicity adjustment will be applied to the multiple dose and multiple endpoints comparisons.

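### The MCP-Mod arm estimates are shown only after a positive test, with 90% CIs that make no stated allowance for model selection; if these are ordinary single-model intervals, coverage with 10 per arm can fall well below 90%

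*SAP*

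**What the plan says.** The Dose-Response Analysis in SAP 3.4.1 sets out an MCP-Mod procedure for the primary endpoint. On the candidates it says: "The models include a linear model, a logistic model, a quadratic model and an Emax model". The dose axis is coded 0, 1, 2, 3.

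Estimation is gated: "If a dose-response relationship exists, then the primary efficacy endpoint will be estimated in each of the treatment groups using the selected dose-response models". The closing sentence then reads: "Point estimates and the corresponding 90% CIs from the selected dose-response models will be displayed". SAP 3.1.5 sets the level, since "all statistical tests and confidence intervals will be based on a 2-sided alpha of 0.10".

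The section does not say how a model is selected, whether one or several are kept, whether they are averaged, or how the intervals are computed. It says that "The MCP-Mod procedure requires pre-specified parameter estimates for the candidate models based on available information" but lists no values. On software it says only that "The procedure will be carried out by the R package MCPMod", with no options. The protocol has no MCP-Mod text to fall back on; SAP section 6 records the analysis as an addition.

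Separately, the UPCR Change from Baseline part of SAP 3.4.1 gives MMRM differences between each dose and placebo with 90% CIs, whatever the MCP-Mod result.

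**The concern.** The same four arms of 10 subjects are used three times: to pass the test, to choose the curve and to estimate the arms. A 90% CI computed from the chosen curve alone treats that curve as if it had been fixed beforehand. With 10 per arm the two-parameter linear model is often chosen even when it is wrong, and its interval is then narrow and off-centre.

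The gate adds a second distortion. When the drug has no effect, the display appears only in false-positive trials, where the estimates are exaggerated by construction.

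This is a dose-ranging trial, and the fitted curve is a natural aid to reading effect by dose. Its intervals may look tighter than the MMRM ones partly because selection uncertainty was left out.

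**Working it through.** **Inputs from the documents.** Protocol 9.4: "Assuming the standard deviation (SD) for the change from baseline in the logarithmic transformation of UPCR is 0.70". The design has 10 per arm and four arms; the candidates and dose codes are those above; the level is 90%. The illustrative ratio of 0.5 (log difference -0.693) comes from the sample size sections.

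**The plan's own figure.** Half-width = t(0.95, 18 df) x 0.70 x sqrt(2/10) = 1.734 x 0.313 = 0.543. For a ratio of 0.5 the CI is 0.5 x exp(-0.543) to 0.5 x exp(0.543), or 0.29 to 0.86. Both agree with the stated figures. They require 0.70 to be the per-subject SD, as the protocol words it. A pairwise interval is therefore 2 x 0.543 = 1.09 wide, or 2 x 0.529 = 1.06 with 36 df.

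**The mechanism by hand.** Suppose the linear model is chosen on the 0-3 axis.
- The sum of squared dose deviations is 10 x (2.25 + 0.25 + 0.25 + 2.25) = 50, so SE(slope) = 0.70/sqrt(50) = 0.099.
- The 90% half-width for 5 mg versus placebo is 1.686 (t, 38 df) x 0.099 = 0.167, a width of 0.33 against 1.06 pairwise.
- Let the true log reductions be 0, 0.05, 0.60, 0.69. The expected slope is (-0.5 x 0.05 + 0.5 x 0.60 + 1.5 x 0.69)/5 = 0.262.
- The 5 mg estimate is then off by 0.262 - 0.05 = 0.212, more than the half-width. Coverage is about Phi((0.167 - 0.212)/0.099) = Phi(-0.45), roughly 32%.
- If the truth is linear, the same interval is centred correctly.

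**Simulation.** Assumed, because the SAP gives none: guesstimates, true shapes, a one-sided 5% test, selection among significant models by AIC or by the largest contrast t (maxT), and delta-method intervals that treat the chosen model as fixed. Guesstimates were varied. The main set was Emax ED50 0.6, logistic 1.5/0.3 and quadratic -0.22; two further sets had ED50 0.2 and 1.5 with matching changes. Shape values differ slightly between runs. The table gives coverage of the nominal 90% CI for 5 mg minus placebo in significant trials, with a ratio near 0.5 at the best dose.

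| True shape | AIC | maxT |
|---|---|---|
| Linear | 86-88% | 88% |
| Plateau from 5 mg | 59-75% | 84-89% |
| Effect only at the two higher doses | 32-37% | 53-77% |
| Umbrella | 67-81% | 81-85% |

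In one AIC run of the third shape, the linear model was chosen in 68% of significant trials and the 5 mg interval averaged 0.54 wide.

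**Other arms and effects.** At this effect size, 15 mg minus placebo covers 84-96%. The 10 mg difference covers 87-96% in most shapes, but 1-76% when only 15 mg twice daily is active and 69-76% when 5 mg is best. At a ratio of 0.7 (main set, maxT), 5 mg is the worst arm in only 2 of 8 shapes; with 5 mg best, coverage at 5/10/15 mg is 88/50/71%.

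**Model choice or gate?** At a ratio of 0.5 most of the loss comes from model choice. With an Emax truth and AIC, the 5 mg difference covers 48-49% over all trials, significant or not, while model-free pairwise CIs still cover 87-94% in significant trials. Under no effect the gate matters too: in the 5% or so of trials that display results, average reductions were 26-45% and only 9-27% of AIC-based CIs contained zero. Pairwise CIs in those trials cover only 29-74%.

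**The remedy.** Bootstrap with AIC re-selection in each resample covered 85-96% in significant trials across the four non-null shapes. Shown whatever the test result, it covered 86-94% over five scenarios including no effect. In false-positive trials alone it covered only 17-53%, so the bootstrap does not cure the gate.

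**The case against.** The strongest objection is that the SAP does not say the intervals come from one model treated as known. It names neither a selection rule nor a CI method, and its plural (models) leaves averaging open. That is correct, and the conclusion is therefore conditional. Silence is still not an adjustment; if averaging is intended, it has to be written down.

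A reader might infer that coverage is far below 90% in general and always worst for 5 mg. The figures do not support that. Coverage is close to nominal for a large linear effect, 15 mg is mostly near nominal at a ratio of 0.5, maxT is milder than AIC in several shapes, and the worst arm changes with shape and effect size. The SAP also speaks of estimates in each group. For the 5 mg arm mean, coverage at a ratio of 0.5 was 65-94% with AIC and 74-96% with maxT, which is milder than for the differences.

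A reader might also take the MCP-Mod output to be the trial's only model-based estimate by dose. It is not. The MMRM contrasts are model-based, primary and reported regardless, and neither document makes MCP-Mod the basis for choosing a dose. The trial is declared exploratory, with no multiplicity adjustment. This limits the consequence but does not make a stated 90% interval correct.

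Finally, the poor coverage in false-positive trials follows from conditioning on significance, which also harms pairwise intervals. That is why the gate itself has to go.

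**Conclusion.** The point holds in conditional form. Estimation is gated on the test, and no allowance is stated for selection or for the gate. Under ordinary single-model intervals, 5 mg versus placebo coverage in significant trials spans about 32-88% (AIC) and 53-89% (maxT) over the four shapes tabulated.

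These figures rest on assumed guesstimates, shapes and selection rules, on a per-subject log SD of 0.70, and on simple arm means without repeated measures, covariates or missing data. The direction is firm; the exact size is not. Only the supplementary dose-response-curve estimates are affected. A change is worth making because it is cheap and gives a better-behaved interval.

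**What to change.** Replace the last paragraph of the Dose-Response Analysis in SAP 3.4.1 with text to this effect:
- Dose-response estimates are averaged over the four candidate models by bootstrap. In each resample all four models are refitted and one is selected by a named criterion, such as AIC.
- The 5th and 95th percentiles of the resampled estimates form the 90% CI.
- The estimates are displayed whether or not the MCP test is significant. Selection must then run over all four candidates, not only those with a significant contrast. The sentence that makes estimation conditional needs the matching edit.
- The MMRM contrasts are the reference estimates for each dose.

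The guesstimates that the SAP says are required should be entered at the same time, because the test depends on them.

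The cost is a paragraph of SAP text and a short bootstrap program, with no change to trial conduct. The intervals widen to about 0.8-1.0 on the log scale, close to the pairwise width of about 1.05-1.09. The curve then adds little precision beyond the MMRM.
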